2 BACKGROUND AND RATIONALE

2.1 Background on Condition, Disease, or Other Primary Study Focus

Nearly all individuals with Down Syndrome (DS) will develop Alzheimer's Disease (AD), some beginning as early as age 30. To date, trials have failed to identify any drug that is safe or effective for the prevention of AD in adults with DS, and there is a lack of non-pharmacologic strategies for the prevention of AD in adults with DS. Previous research in typically developing adults suggests that increased MVPA may improve cognitive function and protect against age-related functional and structural brain changes; however, the potential impact of increased MVPA on the development of AD in adults with DS has not been evaluated. Despite the potential positive impact of MVPA, participation in MVPA among adults with DS is low. The limited research evaluating intervention strategies for increasing MVPA in adults with DS is not specific to adults with DS, i.e., includes all IDDs, and has been unsuccessful in increasing short-term (≤ 12 wks.) or long-term MVPA (12 mos.). Results from our 12-wk. pilot trial of a remote method which delivers real-time MVPA, led by a trained health educator, to groups of adults with DS in their homes (n=27), via video conferencing on a tablet computer demonstrated high attendance, increased MVPA during group sessions, and improvements in cognitive function. However, the sustainability, impact on total daily MVPA, optimal session frequency, and potential impacts on cognitive function and measures of brain health of remotely delivered group MVPA sessions in adults with DS are unknown.

Therefore, we will conduct a 12 mo. early stage clinical trial in 80 non-demented adults with DS to determine the feasibility and potential efficacy of remotely delivered group MVPA, delivered at two different frequencies to increase daily MVPA, relative to a usual care control. This early stage clinical trial will inform and advance the design of a subsequent late stage clinical trial while providing important data regarding the effect of MVPA on cognition and measures of brain health related to development of AD in adults with DS.

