8 STATISTICAL CONSIDERATIONS

8.1 Sample Size and Randomization

Eighty participants will be randomized in a 2:2:1 manner to RH (n=32), RL (n=32) and UC (n=16), respectively. We except a standard deviation in daily MVPA of ~ 10 min. for our primary endpoint (12 mos.) based on 12 mo. data from adults with DS who participated in our weight management trial in adults with IDD (DK83538, PI [name]). We will be able to estimate the mean MVPA at each time point (baseline, 3, 6, 9 and 12 mos.) with 99% confidence within ± 5 min. for the RH and RL groups with 32 participants, and with 98% confidence with 24 participants, i.e. allowing for a 25% loss to follow-up. We will be able to estimate the mean MVPA at each time point with 94% confidence within ± 5 min. for the UC group with 16 participants, and with 89% confidence with 12 participants, i.e. allowing for 25% loss to follow-up). Thus, we will have precision to estimate the intervention effects even with a 25% loss to follow-up.

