8.1.1 Treatment Assignment Procedures

Cohorts of ~10-20 participants will be recruited and computer randomized. Participants will be stratified by sex and age (18-30 or >30) and then sequentially randomized by the study statistician with 2:2:1 allocation to the RL, RH, and UC arms.

This randomization scheme was selected to include more participants in the group video conferencing arms which, if successful, will be included in a later stage trial examining the effectiveness of increased MVPA using the video conferencing approach on cognitive function and brain health in adults with DS.

Intervention assignments will be concealed in envelopes and delivered to the study coordinator. Participant randomization will be stored on the study Redcap Database.

The study team and the participants will not be blinded to group assignment.

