8.3 Data Analyses

Our primary aim is to assess daily MVPA (min.) among the RL, RH, and UC arms at baseline, 3, 6, 9, and 12 mos. and obtain effect sizes for change in MVPA over 12-mos. We will calculate the mean and standard deviation and 95% confidence intervals of daily MVPA at each time point for all 3 groups, as well as for the change from baseline to each time point. This descriptive information will be summarized graphically which will aid in determining if, and when, differences in MVPA arise among and across the 3 groups. The corresponding effect sizes at each time point will be calculated as the differences in the mean divided by the common standard deviation. We will also estimate the correlation of MVPA over time within individuals. This information will be critical to identifying whether single point in time or longitudinal assessments will be utilized to identify the sample size needed for future large-scale confirmatory trials. We will subsequently run a repeated measures ANOVA comparing the change in baseline at each time point across the three groups using a linear mixed model approach with an autoregressive correlation structure over time. The model will include a main effect of group and time and a group by time interaction which will provide an estimate of the treatment effect when modeling longitudinally. The data from this trial will provide solid preliminary data to determine the potential for an effect and inform the best design to employ in subsequent trials.

Our first secondary aim will assess the impact of MVPA across the RL, RH, and UC arms on cardiovascular fitness, quality of life, cognitive function, and brain parameters (whole and regional brain volume, functional connectivity, cerebral blood flow) at baseline, 6, and 12 mos. We will estimate the correlation of change in MVPA on changes in cardiovascular fitness, quality of life, cognitive function, whole and regional brain volume, functional connectivity and cerebral blood flow at 6 and 12 mos. This analysis will be completed with the total sample, irrespective of study arm. Thus 80 participants will provide at least 80% power to detect correlation of 0.31 or higher or -0.31 or lower with a type I error rate of 5%. Sixty subjects (25% loss to follow-up) will still allow us to detect a correlation of 0.36 or higher or -0.36 or lower with 80% power and type I error rate of 5%.

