Our second secondary aim will determine the feasibility (retention, session attendance, use of recorded sessions (RH/RL only), and safety) of RL, RH, and UC arms. We will estimate the proportion of participants retained, session attendance, use of recorded sessions and safety, i.e. significant adverse events across the 12 mo. trial, the proportion that adhere to treatment within each arm. Within the RL and RH arms, 32 participants allow us to estimate these proportions with a margin of error no greater than 0.09. Within the UC group, 16 participants will allow us to estimate these proportions with a margin of error no greater than 0.125.

For all analysis we will explore the impact of demographic characteristics such as gender, and racial/ethnic subgroups.

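### The longitudinal MVPA model analyses change from baseline without baseline MVPA as a covariate; with equal SDs this gives up 35%, 25%, 15% or 5% of arm-contrast variance at an assumed correlation of 0.3, 0.5, 0.7 or 0.9

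*Combined protocol and SAP*

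**What the plan says.** Section 8.3 first describes MVPA by arm and visit and calculates effect sizes from differences in means. It then plans a repeated measures analysis "comparing the change in baseline at each time point across the three groups using a linear mixed model approach with an autoregressive correlation structure". The terms are listed in one sentence: "The model will include a main effect of group and time and a group by time interaction". The plan gives this model a specific job, "which will provide an estimate of the treatment effect when modeling longitudinally". No section names baseline MVPA as a covariate or constrains the arms to a common baseline mean.

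The only other covariate statement is exploratory: "For all analysis we will explore the impact of demographic characteristics such as gender", together with racial/ethnic subgroups. Section 8.1.1 says of the allocation: "Participants will be stratified by sex and age (18-30 or >30) and then sequentially randomized by the study statistician". Section 5 agrees, but the précis and Section 4.3 name sex alone.

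On the quantities that decide how much this matters, Section 8.1 gives one SD, for month 12: "We except a standard deviation in daily MVPA of ~ 10 min. for our primary endpoint (12 mos.) based on 12 mo. data". No baseline SD, SD of change or correlation is given. The correlation is something the trial will produce: "We will also estimate the correlation of MVPA over time within individuals".

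**The concern.** With a change score, the coefficient on baseline is fixed at 1 whatever the data show. Unless the true regression slope of follow-up on baseline is 1, part of any chance imbalance in baseline MVPA stays in the arm contrast. This adds variance and does not bias the contrast. Covariate adjustment estimates the slope and removes that part.

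The trial is one of estimation, and Section 2.1 says of its purpose: "This early stage clinical trial will inform and advance the design of a subsequent late stage clinical trial". Precision of the arm differences is therefore its main product. It is scarcest against Usual Care, with 16 randomized and 12 expected after 25% loss. Section 8.1 gives precision for single-arm means only, so the plan does not show how wide an arm contrast will be.

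Two lesser points sit in the same paragraph of the plan. The randomization factors are left out of the model. And an autoregressive structure is named without saying whether variances may differ by visit or whether a subject effect is included.

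**Working it through.** **The plan's own figures.** Section 8.1 says each arm mean will be within ±5 min with 99%, 98%, 94% and 89% confidence at n = 32, 24, 16 and 12, with SD 10. Using Student's t with n−1 df at 5/(10/√n), I get 99.2%, 97.8%, 93.6% and 88.9%. These reproduce, and nothing below affects them.

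**Inputs.** Follow-up SD s = 10 min (Section 8.1). Arms 32/32/16, or 24/24/12 after 25% loss (Section 8.1). Assumed, because the documents give neither: rho, the correlation between baseline and the visit compared, at 0.3 to 0.9; and k = baseline SD / follow-up SD, at 0.85, 1 and 1.2.

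**Variance of an arm contrast at one visit**, per factor s²(1/n₁ + 1/n₂):

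- change score: 1 + k² − 2·rho·k
- baseline-adjusted, common slope: 1 − rho²
- difference: (k − rho)², which is zero when rho = k
- share removed: (k − rho)² / (1 + k² − 2·rho·k), which is (1 − rho)/2 at k = 1. The allocation ratio cancels.

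Example at k = 1, rho = 0.5: change 1 + 1 − 1 = 1.00; adjusted 1 − 0.25 = 0.75; share removed 25%.

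| k | rho 0.3 | 0.5 | 0.7 | 0.9 |
|---|---|---|---|---|
| 1 | 35% | 25% | 15% | 5% |
| 0.85 | 25% | 14% | 4% | 1% |
| 1.2 | 47% | 40% | 33% | 32% |

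At k = 1 the same loss, expressed as extra participants (for example 1.00/0.75 − 1), is 54%, 33%, 18% and 5%.

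**Cost of estimating the slope.** With three arms the adjusted variance is multiplied by 1 + 1/(N − 5): 1.0133 at N = 80 and 1.0182 at N = 60. The k = 1 row becomes 34%, 24%, 14%, 4% at 80 and 34%, 24%, 13%, 3% at 60. At N = 80 the k = 0.85 row becomes 24%, 13%, 3%, 0%. Simulation of 32/32/16 trials at k = 1 (40,000 trials) gave 34.2%, 24.0% and 13.8% at rho 0.3, 0.5 and 0.7.

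**95% half-width, Remote High vs Usual Care, 24 vs 12.** t(0.975) × 10 × √[variance term × (1/24 + 1/12)], two arms, 34 df for change and 33 for adjusted. In minutes, change then adjusted:

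| k | rho 0.3 | 0.5 | 0.7 |
|---|---|---|---|
| 1 | 8.5 → 6.9 | 7.2 → 6.2 | 5.6 → 5.1 |
| 0.85 | 7.9 → 6.9 | 6.7 → 6.2 | 5.2 → 5.1 |
| 1.2 | 9.4 → 6.9 | 8.0 → 6.2 | 6.3 → 5.1 |

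At k = 1 and rho 0.9 it is 3.2 → 3.1. Estimating the slope (factor 1 + 1/32) adds about 0.1 min or less to the adjusted values.

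**If the response is read as raw MVPA at all five visits**, unconstrained arm-by-visit means give the same change contrast with complete data, so the loss is unchanged.

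**Covariance (secondary).** Here r is the correlation between adjacent visits, a different quantity from rho above. I derived the 4×4 covariance of the change scores and fitted a homogeneous AR(1) to it. If raw MVPA is AR(1) with r = 0.3, 0.5, 0.7, the model SE over the true SE is 0.94, 0.90, 0.85 at month 12 and 1.12, 1.23, 1.35 at month 3. If raw MVPA is equally correlated across visits, the ratio is 1.00 at every visit.

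**The case against.** The strongest objection concerns size. The formula 1 − rho² assumes the same baseline slope in every arm. An intervention that changes activity in two arms could flatten their slopes, and the pooled slope is dominated by those arms. In simulations of 32/32/16 with equal SDs, slopes of 0.5 in the remote arms and 0.9 in Usual Care cut the gain for Remote High vs Usual Care to about 1–2%. That stands, so near-zero gain is not confined to k = 0.85 with rho = 0.9. It needs a large gap, though: with 0.5 and 0.7 the gain is still about 15%. In the worst case tried (0.3 and 0.9), adjustment cost about 1% or less.

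Second, the equal-SD row is one choice among several. Section 4.2 excludes regular exercisers, which could make k less than 1. This is fair, and the k = 0.85 row should be read beside it.

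Third, little hangs on this model: descriptive effect sizes come first, no alpha or go/no-go rule is attached, and a later planner could derive the adjusted variance from the reported SDs and correlations. That limits the consequence to precision. A later planner's calculation would not narrow this trial's own reported intervals.

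Fourth, the covariance point is a different harm: standard errors too small at month 12 and too large at month 3, not simply wider intervals. That is correct. It depends on a correlation pattern the documents do not give and on change scores being the modelled response, so it is kept secondary. The inconsistent stratification wording is likewise a separate matter of documentation, and its effect on precision cannot be sized.

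**Conclusion.** The concern holds. As written, the longitudinal estimate omits a covariate scheduled for collection on everyone and gives up precision. At a single visit the loss runs from about zero to 47% of the contrast variance over the ranges examined, and is 35%, 25%, 15% or 5% with equal SDs at rho 0.3, 0.5, 0.7 or 0.9. These figures rest on assumed rho and k, a common slope across arms and complete data at the visit. The contrast stays unbiased, and no test or decision rule is invalidated. Confidence is high that the covariate is absent and that adding it is sensible. The exact gain cannot be known until the trial's own correlation and baseline SD are seen. The change should be made, but it is not critical.

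**What to change.** Reword the longitudinal model in Section 8.3:

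- Response: MVPA at 3, 6, 9 and 12 months.
- Terms: arm, visit, arm-by-visit, baseline MVPA, baseline-by-visit, sex and age group (18–30 / >30).
- Covariance: name it. For example, unstructured with a Kenward-Roger correction, and a prespecified simpler structure with small-sample-corrected robust standard errors if it does not converge.
- Reporting: baseline-adjusted arm differences with 95% intervals beside the descriptive effect sizes already planned.

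State the stratification factors identically in the précis and Sections 4.3, 5 and 8.1.1.

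The cost is wording only. The model gains 6 mean parameters (4 baseline-by-visit, 2 strata) on top of 12 arm-by-visit means. At any one visit it uses 6 (3 arms, baseline, sex, age), leaving about 80 − 6 = 74 between-person df, or 60 − 6 = 54 after 25% loss. The main risk is non-convergence of an unstructured covariance with about 12 Usual Care completers, which the fallback covers.

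### The longitudinal model takes change from baseline as its outcome but names the group-by-time interaction as the treatment effect; on change scores that term only shows whether the arm difference varies between visits.

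*Combined protocol and SAP*

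**What the plan says.** Section 8.3 (Data Analyses) handles the primary outcome in two steps. The first is descriptive: means, SDs and 95% CIs of daily MVPA for each arm at each visit, "as well as for the change from baseline to each time point". Standardised differences follow: "The corresponding effect sizes at each time point will be calculated as the differences in the mean divided by the common standard deviation".

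The second step is the model: "We will subsequently run a repeated measures ANOVA comparing the change in baseline at each time point across the three groups". Its covariance form is also given, if briefly: "using a linear mixed model approach with an autoregressive correlation structure over time". On its terms: "The model will include a main effect of group and time", together with "a group by time interaction which will provide an estimate of the treatment effect when modeling longitudinally".

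Section 8.3 names no contrast, visit, alpha or decision rule for this model, and does not say whether baseline is kept as a level of time. Section 8.1 does single out a visit; it gives the expected SD "for our primary endpoint (12 mos".

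**The concern.** Where baseline belongs decides which term carries the treatment effect. If raw MVPA is the outcome and baseline is the first level of time, the arms start equal in expectation and the effect appears as a group-by-time interaction. If baseline has been subtracted and only months 3, 6, 9 and 12 remain, the effect is the arm difference in mean change, which is the group term plus the interaction term for that visit. Section 8.3 pairs the second outcome with the term that suits the first.

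This is the only planned between-arm model of the primary outcome. The 95% CIs in the descriptive step are attached to each arm's means and changes; none is stated for the between-arm effect sizes. A later team looking for a modelled treatment effect would be directed to a term that is zero when the benefit is held from month 3 to month 12, and non-zero when the benefit appears early and is lost.

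**Working it through.** **What the interaction measures.** Let d(v) be the RH–UC difference in mean change at visit v, for v = 3, 6, 9, 12. The model writes d(v) = g + i(v), where g is the group term and i(v) the interaction term. With month 3 as reference, g = d(3) and i(12) = d(12) − d(3). Under any coding, the interaction depends only on differences between the d(v).
- Sustained effect, d(v) = D at all four visits: i(12) = D − D = 0, whatever the size of D.
- Effect fading from D at month 3 to nothing at month 12: i(12) = 0 − D = −D, although d(12) = 0.

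**With baseline as a time level (raw MVPA).** The month-12 interaction contrast is [RH(12) − RH(0)] − [UC(12) − UC(0)] = d(12), which is the treatment effect.

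**The plan's own figures.** Section 8.1 gives confidence levels for estimating one arm's mean within ±5 min at SD 10. Using 2·T(5√n/10; n − 1 df) − 1, the results are 99.2% (n = 32), 97.8% (24), 93.6% (16) and 88.9% (12), against 99, 98, 94 and 89% stated. They reproduce. They describe single arms; no precision or power is given for any between-arm contrast.

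**Inputs for the size of the problem.**
- From section 8.1: SD 10 min/day; arms 32/32/16, or 24/24/12 after 25% loss.
- From section 5 (Homework assignments): potential session minutes of 90 per week for RH and 30 for RL. 90/7 = 12.9 and 30/7 = 4.3 min/day. These are taken as upper bounds on the effect, with UC at 0.
- Assumed, not in the documents: AR(1) correlation ρ = 0.3 to 0.7 between successive visits of raw MVPA, 5% two-sided tests, and linear fading.

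**Month-12 RH–UC contrast, sustained effect.** Months 0 and 12 are four steps apart, so the SD of change is √[2·100·(1 − ρ⁴)]. This is 14.08 at ρ = 0.3 and 12.33 at ρ = 0.7.
- 32/32/16: SE = SD·√(1/32 + 1/16) = 4.31 and 3.78. Power = Φ(12.9/SE − 1.96) = 85% and 93%.
- 24/24/12: SE = SD·√(1/24 + 1/12) = 4.98 and 4.36. Power = 74% and 84%.

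**Group-by-time test on change scores** (3 arms, 4 visits, 6 df; Wald test with known covariance):

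| True effect | Interaction rejects, 32/32/16 | Interaction rejects, 24/24/12 | Month-12 RH–UC rejects |
|---|---|---|---|
| Sustained 12.9/4.3/0 | 5% at every ρ | 5% at every ρ | 85–93% (74–84% at 24/24/12) |
| Fading 12.9/4.3/0 to zero | 70–87% | 55–75% | 5% |
| Fading from 10 min/day in RH, and 5 or 10 in RL, to zero | about 39–63% | 30–49% | 5% |

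Simulation with a fitted AR(1) at 32/32/16 lowers the last row's interaction rate to 19–56%. The fading figures therefore depend on the assumptions; the 5% for a sustained effect does not.

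**How far the two readings diverge.** For a sustained +10 min/day in both RH and RL at 32/32/16, the interaction on change scores rejects 5% of the time. The group main effect on the same scores has 85–96% power. The interaction on raw MVPA with baseline as a level (8 df) has 67–95%.

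**The case against.** The strongest reply is that the primary aim is estimation in an early-stage trial. The month-12 mean changes and standardised differences are already planned and come before the model. The model contains the group main effect, so a sustained benefit would be visible in two places. No alpha, hypothesis or go/no-go rule is tied to the interaction. All of this stands. A reader might infer that a sustained benefit would be reported as no effect and a vanished one as a clear effect; the documents do not support that, because they neither rest a conclusion on the interaction nor suppress the other results.

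Second, "comparing the change in baseline at each time point across the three groups" is loose wording and may mean raw MVPA with baseline as a time level, where the interaction does carry the effect. This is possible, but the same paragraph has just described change from baseline to each visit, so change scores are the natural reading. If raw MVPA was meant, the outcome is misdescribed, and an omnibus 8-df interaction is still not the month-12 difference. If the clause refers to the whole model rather than the interaction, no contrast has been named. The text needs an edit on every reading.

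Third, the effect may build rather than stay flat. Section 5 raises the target to 150 min/wk only at the start of month 4, after the first follow-up visit, so a non-zero interaction is plausible. That is fair, but the interaction then captures only growth since month 3. With RH building from 2.5 to 10 min/day and RL at half that, it rejects in 22.5–32.3% of trials, against 64–76% for the month-12 RH–UC contrast (32/32/16).

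Fourth, the session minutes are what sessions could provide, and UC shares the MVPA target and the support sessions. They are used here only as a ceiling, with 10 min/day shown beside them.

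**Conclusion.** As written, the sentence misidentifies the estimand. That follows from algebra and needs no assumption beyond the outcome being change at months 3 to 12: a constant arm difference makes the interaction exactly zero. The opposite error is possible but not assured: a fading effect can give a significant interaction, at rates that vary widely with effect size, correlation, retention and how the covariance is handled.

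The consequence is bounded. The planned output would still show a sustained effect, so the defect is a wrong label on the one between-arm model of the primary outcome, with no month-12 contrast named although section 8.1 treats 12 months as the primary endpoint. It should be corrected before analysis, since the two readings of the outcome give very different answers for a sustained benefit.

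**What to change.** In section 8.3, replace the clause on the interaction with text to this effect: the treatment effect is the model-based difference between arms in mean change at month 12 (RH–UC, RL–UC, RH–RL), each with a 95% CI; the same contrasts at months 3, 6 and 9, and averaged over the four visits, are supportive; the group-by-time interaction is reported only as a check of whether the effect changes over time. State that the outcome is change from baseline at the four follow-up visits.

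If raw MVPA with baseline as a time level was intended, say so and report the month-12 group-by-time contrast, meaning the arm difference in change from baseline to month 12, rather than the omnibus interaction.

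Either version costs a few lines of analysis-plan wording. The data and visits do not change; only the stated outcome and the requested contrasts do.

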1.2 Secondary Objectives

Secondary aim 1: Assess the impact of MVPA across the RL, RH, and UC arms on cardiovascular fitness, quality of life, cognitive function and brain parameters related to AD (whole and regional brain volume, functional connectivity, cerebral blood flow) at baseline, 6, and 12 mos.

Secondary Aim 2: Determine the feasibility (retention, session attendance, use of recorded sessions (RH/RL only) and safety of RL, RH, and UC arms.

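### Secondary Aim 1 is phrased across the randomized arms, but its only prespecified analysis is a correlation pooled over arms; no by-arm summary or randomized contrast is planned for fitness, cognition, quality of life or brain outcomes

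*Combined protocol and SAP*

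**What the plan says.** Section 1.2 states the aim as "Assess the impact of MVPA across the RL, RH, and UC arms on cardiovascular fitness, quality of life, cognitive function and brain parameters", with assessments at baseline, 6 and 12 months.

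The analysis is in Section 8.3: "We will estimate the correlation of change in MVPA on changes in cardiovascular fitness, quality of life, cognitive function" and the brain measures, at 6 and 12 months. It adds: "This analysis will be completed with the total sample, irrespective of study arm". The sample size is justified for that correlation alone: "Thus 80 participants will provide at least 80% power to detect correlation of 0.31 or higher", and "Sixty subjects (25% loss to follow-up) will still allow us to detect a correlation of 0.36 or higher".

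The same section sets out a full by-arm plan for daily MVPA: means, SDs and confidence intervals by arm, standardized effect sizes, within-person correlation over time, and a linear mixed model with group, time and their interaction. None of this is extended to the Secondary Aim 1 outcomes. The one further statement that reaches them, at the end of Section 8.3, is a general promise to explore demographic characteristics, with gender and racial/ethnic subgroups as examples. It names neither age nor arm and gives no adjustment model.

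**The concern.** Change in MVPA is something participants do after randomization. Correlating it with change in cognition or fitness compares people who became more active with people who did not, and randomization does not protect that comparison. The documents themselves suggest a confounder: Section 2.1 says Alzheimer's disease can begin as early as age 30 in this population, and Sections 5 and 8.1.1 stratify randomization at age 30. Age could plausibly influence both activity change and cognitive or brain change. Pooling without regard to arm also folds in any effect of group contact that does not act through MVPA.

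Two things are at stake. A non-zero pooled correlation may be reported as an *impact* of MVPA. Also, Sections 5 and 8.1.1 say the allocation was chosen with a later trial on cognition and brain health in view, yet the arm-level effect sizes and SDs which that trial would need on its own endpoints are not planned here.

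**Working it through.** **1. The plan's own power figures (Section 8.3).** Fisher z, two-sided 5%: power = Φ(atanh(r)·√(N − 3) − 1.96).
- r = 0.31, N = 80: 80.3%.
- r = 0.36, N = 60: 81.2%.

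Both stated figures reproduce. The issue is what is estimated, not the arithmetic.

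**2. What is planned for each outcome type (Section 8.3).**

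| Quantity | Daily MVPA | Secondary Aim 1 outcomes |
|---|---|---|
| Mean, SD, CI by arm | yes | not stated |
| Standardized effect size | yes | not stated |
| Group-by-time mixed model | yes | not stated |
| Pooled correlation with change in MVPA | not applicable | yes |

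The data for the empty cells will exist: the schedule in Section 6.1 collects these outcomes at baseline, 6 and 12 months, with imaging in a sub-sample.

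**3. How far confounding could move the correlation.** Suppose age correlates a (in absolute value) with both changes, and the two changes are otherwise unrelated. The pooled correlation then has absolute size a². The documents give no value for a, so a range is shown. The two-sided rejection rate at N = 80 is Φ(atanh(a²)·√77 − 1.96) + Φ(−atanh(a²)·√77 − 1.96).

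| a (assumed) | Spurious r = a² | Rejection rate of the 5% test |
|---|---|---|
| 0.1 | 0.01 | 5.1% |
| 0.2 | 0.04 | 6.4% |
| 0.3 | 0.09 | 12.4% |
| 0.4 | 0.16 | 29.4% |

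**4. What an arm contrast would deliver.** 95% half-width in SD units = t(0.975, n1 + n2 − 2)·√(1/n1 + 1/n2), without baseline adjustment, which would tighten it. Arm sizes are from Section 8.1; 25% loss is the plan's own allowance.
- RH or RL versus UC, 32 versus 16: 2.013 × 0.306 = 0.62.
- RH or RL versus UC after 25% loss, 24 versus 12: 2.032 × 0.354 = 0.72.
- RH versus RL, 32 versus 32: 0.50; after 25% loss, 24 versus 24: 0.58.
- RH versus UC for imaging if half are scanned (assumption; the sub-sample size is not given), 16 versus 8: 2.074 × 0.433 = 0.90.

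Power for RH versus UC at an assumed difference of 0.5 SD is about 37% with the full sample, so these contrasts serve as estimates rather than tests.

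**The case against.** **The wording of the aim.** Its exposure is MVPA, not assignment, and *across* the arms can mean spanning them. On that reading a pooled change-on-change analysis is what was asked for. This stands as a reading of the aim. It does not turn the correlation into evidence of impact, which is a causal term.

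**The arm contrast does not isolate MVPA either.** Table 1 gives all arms the same weekly MVPA recommendation and support schedule, so group sessions and their frequency are what separate them, and a contrast carries their social content too. This stands, and the contrasts should be described accordingly. The text of Section 3 gives support-session frequencies that differ by arm and disagree with Table 1. The two must be reconciled, because this changes what a contrast contains.

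**The confounding range.** Change scores already remove stable differences in level, so age would have to predict change in both quantities. At a = 0.1 to 0.2 the error rate is close to nominal. This stands, and the size of the problem is unknown.

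**Early-stage purpose.** Section 2.1 frames the trial around feasibility and raising daily MVPA. That excuses low power. It does not explain omitting by-arm estimates, since the primary aim is itself estimation.

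**Stronger readings that the documents do not support.** A reader might infer that the trial can yield no randomized estimate for these outcomes. It prespecifies none, but the data collected would allow one. A reader might also infer that every covariate is ignored. Section 8.3 does promise open-ended demographic exploration, though without a commitment to adjust.

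**Conclusion.** The point holds as a gap in prespecification. For Secondary Aim 1 the plan contains no by-arm summary and no randomized contrast, and its single analysis is an unadjusted observational association. Its possible distortion depends on an undocumented quantity: rejection with no true link runs from about 5% to 29% as the assumed age correlation goes from 0.1 to 0.4, so a serious inflation is possible but not shown.

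Arm contrasts would be valid for the effect of assignment but imprecise, at about 0.62 SD either side for RH versus UC with everyone observed. It would be tempting to call them unbiased throughout. At 24 versus 12 that requires a missing-data assumption, because randomization does not guarantee an unbiased comparison of completers. The half-widths from the full arms do not carry over to imaging, and neither do the N = 80 and N = 60 power figures. The gap should be closed in the plan; it does not invalidate the trial.

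**What to change.** In Section 8.3, for each Secondary Aim 1 outcome:
- Add the by-arm means, SDs and standardized effect sizes, and the group-by-time mixed model already written for MVPA, adjusted for the baseline value, sex and age group.
- Report RH − UC, RL − UC and RH − RL differences at 6 and 12 months with 95% confidence intervals. Describe them as effects of assignment (group sessions and their frequency), not of MVPA alone.
- State the missing-data assumption under which these estimates are valid.
- Keep the correlation as a supportive analysis, adjusted for arm, age and sex, and call it an association.
- State the planned size of the imaging sub-sample and give precision for it separately.

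The cost is a few paragraphs of plan text and some extra models on data already being collected, with no added visits or participants. The downside is wide intervals, especially for imaging, so the contrasts should be presented as estimates to inform the later trial.
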